- Attempted suicide or adverse event associated with an increase in suicidal ideation to a 4 or 5 on the C-SSRS will be reported as an AESI by the PI within 24 hours of discovery and will be followed until the outcome of the event(s) is known, refer to Section 10.1.3 Adverse Events of Special Interest (AESI).

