10.0 Safety

10.1 Adverse Events, Serious Adverse Events, Adverse Events of Special Interest and Other **Safety Reporting**

MAPPUSX Protocol

The investigator and any qualified designees are responsible for detecting, documenting, and recording events that meet the definition of an Adverse Event (AE), Serious Adverse Event (SAE), or Adverse Event of Special Interest (AESI), and remain responsible for following up on all AEs.

AEs will be reported by the participant (or, when appropriate, by a caregiver, surrogate, or the participant's legally authorized representative). The collection period of AEs is from the time of signed ICF until the completion of the study termination visit (+/- 2 days). Medical occurrences that begin before the start of Visit 0, but after obtaining informed consent may be recorded as medical history or a current medical conditions, unless the event occurs as a result of a study requirement in which case the event would be reported as an AE. All AEs should be recorded regardless of the cause of the event, whether the event is deemed positive, negative or neutral by the investigator, reporter or qualified designee. The investigator will elicit information through non-leading open-ended questioning and examination of the participant about the occurrence of the AE. For each event, the following information will be recorded in the participant's record and transcribed into the AE section of the eCRF and SAE form when appropriate according to the instructions below:

- Classification of the event: serious or non-serious
- Classification of the event as an adverse event of special interest (AESI)
- Description of signs and/or symptoms. Whenever possible, the specific diagnosis for the event will be recorded. If a diagnosis cannot be made, each sign or symptom will be recorded separately (e.g., nausea and vomiting would be recorded as two separate events).
- Severity of event: mild, moderate or severe
- Relationship to study medication: related or not related
- Action taken with study medication: dose maintained, dose not changed, dose reduced, interruption of dose, drug withdrawn/discontinued, unknown, or not applicable
- Adverse event outcome: resolved without sequelae, resolved with sequelae (describe sequelae), resolving, not resolved, fatal, or unknown (lost to follow-up)
- Event onset date. If a laboratory event is reported as an AE, record the start date as the date of collection of the first lab sample that shows the change.

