10.1.3 Adverse Events of Special Interest (AESI)

An adverse event of special interest (AESI) is a serious or non-serious event of scientific and medical concern specific to the study intervention. The event may require further investigation and depending on the nature of the event, submission to the FDA or other applicable regulatory authorities. For the purpose of this trial, AESIs have been predefined.

AESIs will be reported on the SAE/AESI report form within 24 hours of discovery. Any AESI that also meets the criteria of a SUSAR (suspected unexpected serious adverse reaction) will be emergently reported to FDA and other appropriate regulatory agencies, PIs, IRBs and IECs. AESIs will be followed until the outcome of the event is determined.

AESIs will include the following:

- Cardiac arrhythmias, or AEs that are indicative of QT interval prolongation, including (but not limited to) Torsade de pointes, sudden death, ventricular extrasystoles, ventricular tachycardia, ventricular fibrillation and flutter, palpitations, and non-postural syncope
- Cardiac disorders (e.g., acute MI, angina pectoris, ischemic chest pain)
- Drug diversion, drug abuse and drug accountability (e.g., accidental poisoning, behavioral
 addiction, dependence, drug abuser, drug diversion, overdose, intentional overdose, intentional
 product misuse, poisoning deliberate, prescribed overdose, substance abuser, euphoria-like
 response, hallucination dissociative state, psychosis, aggression, drug tolerance, habituation, drug
 withdrawal syndrome, substance related disorders)

- Central nervous system vascular disorders (e.g., ischemic central nervous system vascular)
- Seizures
- Hypertensive crisis

conditions)

• Suicide, suicidal behavior (e.g., intentional overdose, intentional self-injury, suicide attempt, suicide threat, suspected suicide, suspected suicide attempt), C-SSRS Suicidal Ideation score of 4 or 5, and/or suicidal ideation judged to be serious or severe in the opinion of the investigator

MAPPUSX Protocol

Amendment 3 Version 1: 15 March 2023

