### **3.3 Safety Objectives**

The overall safety objective is to assess severity, incidence and frequency of Adverse Events (AEs), Treatment Emergent AEs (TEAEs), AEs of Special Interest (AESIs), and Serious Adverse Events (SAEs), concomitant medication use, suicidal ideation and behavior, and vital signs to support the package insert for MDMA-assisted therapy. The following safety objectives will evaluate the safety of MDMA-assisted therapy:

1. Assess incidence of AEs during Experimental Sessions that may be indicative of a medical complication of the Investigational Medicinal Product (IMP) such as clinical signs and symptoms of chest pain, shortness of breath, or neurological symptoms or any other signs or symptoms that prompt additional vital sign measurements
2. Assess incidence of AEs by severity
3. Assess incidence of TEAEs by severity
4. Assess incidence of TEAEs by severity reported during an Experimental Session, 1 day, and 2 days after IMP administration
5. Assess incidence of AESIs, defined as AEs specified in the protocol related to cardiac function, suicidality, and abuse liability
6. Assess incidence of AEs by severity categorized as leading to discontinuation of IMP, resulting in death or hospitalization, and continuing at Study Termination
7. Assess incidence of SAEs
8. Assess incidence of concomitant medications taken during an Experimental Session, 1 day, and 2 days after IMP administration
9. Assess incidence of psychiatric concomitant medications taken during the Treatment Period
10. Assess incidence of positive or serious suicidal ideation and positive suicidal behavior assessed with the Columbia Suicide Severity Rating Scale (C-SSRS)
11. Assess changes in blood pressure (BP), heart rate, and body temperature from pre-IMP administration to end of each Experimental Session

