### **8.8.2 Analysis of Adverse Events**

The primary measure of safety will be the reporting of unsolicited AEs. All AEs collected from Enrollment to Termination will be categorized as follows:

- Pretreatment AEs are defined as AEs that occur during the Preparatory Period prior to the first dose in the first Experimental Session
- Treatment Emergent AEs are defined as AEs that occur during the Treatment Period from the first Experimental Session to the last Integrative Session
- AEs that occur on and two days after MDMA administration
- AESIs are defined as AEs specified in the protocol related to cardiac function and abuse liability
- Follow-up Period AEs are defined as AEs that occur during the Follow-up Period after the last Integrative Session through Termination
- AEs leading to discontinuation of IP
- AEs resulting in death or hospitalization.
- SAEs
- AEs continuing at Termination.

Verbatim terms on case report forms will be mapped to preferred terms (PT) and system organ class (SOC) using the Medical Dictionary for Regulatory Activities (MedDRA) Version 24.0. Frequency and incidence of AEs will be displayed by PT, sorted by SOC, severity, and seriousness. AEs will be analyzed and presented as follows:

- If a participant has more than one AE mapped to the same PT, that AE will be reported once using the highest severity
- Relationship will be determined by the Clinical Investigator
- AEs that occur on day of Experimental Sessions and two days after IP administration will be presented separately.

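### SAP 8.8.2 restricts AESIs to cardiac and abuse-liability events, so an AESI summary built from it would omit suicidality, seizures and CNS vascular disorders that Protocol 10.1.3 predefines as AESIs

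*SAP*

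**What the plan says.** The documents describe AESIs in three ways.

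- **SAP 8.8.2**, which sets out how adverse events are categorised for analysis: "AESIs are defined as AEs specified in the protocol related to cardiac function and abuse liability". That is two areas.
- **SAP 3.3, objective 5**, repeated in Protocol 2.3 and the protocol synopsis: "Assess incidence of AESIs, defined as AEs specified in the protocol related to cardiac function, suicidality, and abuse liability". That is three areas.
- **Protocol 10.1.3**: "For the purpose of this trial, AESIs have been predefined". A list of seven groups follows. It includes "Central nervous system vascular disorders", seizures, hypertensive crisis, and a suicidality group that extends to "C-SSRS Suicidal Ideation score of 4 or 5, and/or suicidal ideation judged to be serious or severe in the opinion of the investigator".

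Protocol 9.1 is consistent with 10.1.3 on suicidality. It treats an attempted suicide as an AESI, and likewise an event that involves worsening ideation: "an increase in suicidal ideation to a 4 or 5 on the C-SSRS will be reported as an AESI by the PI".

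Sites work to the protocol list. Under 10.1.3, "AESIs will be reported on the SAE/AESI report form within 24 hours of discovery", and Protocol 10.1 has each event's record carry "Classification of the event as an adverse event of special interest (AESI").

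**The concern.** AESI incidence is a stated safety objective, and the safety data are intended to support the package insert. Sites will classify and report AESIs under seven groups. The only analysis text that defines the category names two areas, so the AESIs reported during the study and those tabulated at the end could disagree.

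The omitted groups are risks that the protocol raises itself. Protocol 9.1 names stroke together with acute myocardial infarction as possible rare complications of the drug's cardiovascular effects. Under 8.8.2 the infarction would count as an AESI and the stroke would not. The same section records that C-SSRS scores rose during Preparatory Sessions in earlier trials, yet suicidality is the area that 8.8.2 drops from the SAP's own objective.

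**Working it through.** No sample-size, power or alpha figure bears on this point. The check compares texts and counts listed groups.

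**Step 1. Match each group in Protocol 10.1.3 to the two shorter definitions.**

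| Group in Protocol 10.1.3 | SAP 8.8.2 | Objective 5 (SAP 3.3, Protocol 2.3) |
|---|---|---|
| Arrhythmia and QT events | covered | covered |
| Cardiac disorders | covered | covered |
| Diversion, abuse and accountability | covered | covered |
| CNS vascular disorders | omitted | omitted |
| Seizures | omitted | omitted |
| Hypertensive crisis | unclear | unclear |
| Suicide, suicidal behaviour, serious ideation | omitted | covered |

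- SAP 8.8.2: 3 covered + 3 omitted + 1 unclear = 7.
- Objective 5: 4 covered + 2 omitted + 1 unclear = 7.
- If hypertensive crisis is read as cardiac function, the covered counts become 3 + 1 = 4 and 4 + 1 = 5.

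Adding only the missing word on suicidality to 8.8.2 would bring it to objective 5, at 4 of 7 (or 5 of 7). Objective 5 is therefore also short of 10.1.3.

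**Step 2. Does the reference to the protocol in 8.8.2 bring in the whole list?** Both 8.8.2 and objective 5 speak of events the protocol specifies, then restrict them by subject area. They use the same phrase with different areas, so the areas carry meaning. On a plain reading the restriction narrows the reference.

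**Step 3. Does other SAP text repair it?**
- SAP 4.3 lists AESIs as a safety measure without defining them.
- The list of summary tables in SAP 8.8 does not name AESIs. Neither does the matching list in Protocol 13.2.2.
- Nothing in the SAP says that the site-recorded AESI classification selects the events.

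**Step 4. Is suicidality recovered elsewhere?** Only in part.
- SAP 8.8.4 summarises C-SSRS responses and counts scores of 4 or 5 as serious ideation. Protocol 10.1.3 also includes ideation that the investigator judges serious or severe, whatever the score.
- The periods listed in 8.8.4 do not name the telephone contacts at which Protocol 7.3.2 also administers the C-SSRS.
- The suicidality group in 10.1.3 names 9 items: suicide (1), examples of suicidal behaviour (6) and ideation criteria (2). Only intentional overdose is also named in the abuse group, which leaves 9 - 1 = 8 in neither area of 8.8.2. The behaviour examples are illustrative, so this shows how little the groups overlap and does not measure events.

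**The case against.** The strongest reply is that an under-count is possible but not certain. Section 8.8.2 refers to events specified in the protocol, the protocol predefines them, and sites record an AESI classification. An analyst who used that classification, and who read objective 5 in the same SAP, would not drop suicidality. That is fair, and the finding is accordingly limited to a summary built from 8.8.2. It does not make 8.8.2 correct: the SAP never tells the analyst to use the classification, and its two definitions disagree.

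A second reply is that little information is lost. All AEs are displayed by preferred term, system organ class, severity and seriousness, with the investigator's assessment of relationship. SAP 8.8 also plans a look at neurological symptoms during Experimental Sessions, where a seizure or stroke in session would be visible. This stands. What is lost is the AESI grouping, and with it the incidence that objective 5 promises. Events outside sessions would not appear in the in-session summary.

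A third reply is that the mapping involves judgement, since the protocol's risk table treats cardiovascular and cerebrovascular events as one risk. This affects the edges, chiefly hypertensive crisis. Seizures and suicidality do not fit either area of 8.8.2 on any ordinary reading.

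Finally, the study has a single arm, and no primary or key secondary endpoint depends on this definition. That limits the weight of the point but does not remove it.

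**Conclusion.** The concern holds. SAP 8.8.2 contradicts the SAP's own objective 5 and is narrower than the predefined list in Protocol 10.1.3. As written it covers 3 of 7 groups, omits 3 and leaves 1 unclear. These are counts of listed groups, not of events, and how many AESIs would be missed cannot be estimated from the documents.

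The conclusion assumes that the summary is programmed from 8.8.2 and that its subject areas are meant as a restriction. The consequence is confined to AESI reporting: the events stay in other outputs, and expedited reporting and participant protection are unaffected. It should be corrected before database lock.

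**What to change.** - **Definition.** In SAP 8.8.2, define AESIs as all events listed in Protocol 10.1.3.
- **Source.** State that the summary uses the AESI classification recorded in the eCRF, reconciled with that list.
- **Display.** Name the AESI table in SAP 8.8 and present it by the seven groups. Because the protocol requires only that an event be classified as an AESI, and not to which group it belongs, the SAP should add a mapping of terms to groups. It also needs a counting rule for events that fit two groups, such as intentional overdose.
- **Objectives.** Align objective 5 in SAP 3.3 with 10.1.3 now. Align Protocol 2.3 and the synopsis when the protocol is next amended, since those changes need the usual approvals.

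The SAP changes alone put the analysis right. They cost revised wording, table shells and a term mapping, with no new data collection. AESI counts may be higher than under the current text.

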## 8.8 Safety Analyses

Safety analyses will confirm safety data with summary tables listing exposure to IMP, unsolicited AEs, TEAEs, concomitant medications, suicidal ideation and behavior, and vital signs overall and by group. If a participant has more than one AE mapped to the same PT, that AE will be reported once using the highest severity. AEs that occur on Day 0 (Experimental Session), Day 1, Day 2

after IMP administration will be presented separately. Compare relative incidence of AEs during Experimental Sessions such as clinical signs and symptoms, such as chest pain, shortness of breath, or neurological symptoms or any other signs or symptoms that may be indicative of a medical complication of the IMP.

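### The SAP has no rule for adverse events that begin before the first dose and worsen after it, and leaves the scope of its once-per-term counting rule and the meaning of frequency undefined

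*SAP*

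**What the plan says.** SAP 8.8.2 assigns AEs to periods. On the pre-dose side: "Pretreatment AEs are defined as AEs that occur during the Preparatory Period prior to the first dose in the first Experimental Session". On the post-dose side: "Treatment Emergent AEs are defined as AEs that occur during the Treatment Period from the first Experimental Session to the last Integrative Session". A follow-up category comes after the last Integrative Session. None of these definitions mentions a change in severity, and Protocol 13.2.2 adds nothing on the point.

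The counting rule is "If a participant has more than one AE mapped to the same PT, that AE will be reported once using the highest severity". It also appears in SAP 8.8 and Protocol 13.2.2, each time without saying whether it works within a table, a period, a session or the whole study.

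The same SAP section promises that "Frequency and incidence of AEs will be displayed by PT, sorted by SOC, severity, and seriousness" and that "AEs that occur on day of Experimental Sessions and two days after IP administration will be presented separately". SAP 8.8 likewise gives a separate display to "AEs that occur on Day 0 (Experimental Session), Day 1, Day 2". The umbrella sentence of SAP 3.3 names severity, incidence and frequency. The numbered AE objectives beneath it ask for incidence.

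**The concern.** The protocol itself expects symptoms before the first dose. Table 9 in Protocol 9.1 says that tapering psychiatric medication can bring new or returning symptoms, and that suicidality scores rose during Preparatory Sessions in earlier trials. Protocol Appendix A says that anxiety and depressed mood are occasionally reported 1 to 3 days after MDMA. The same preferred term (PT) can therefore plausibly be recorded in one participant before and after dosing.

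Unsolicited AEs are the SAP's primary safety measure, and the safety objective is to support a package insert. The study has one arm, so no control group would show that events had been put in the wrong period. If the boundary between pretreatment and treatment-emergent is ambiguous for the very events the protocol anticipates, the TEAE table depends on a programmer's choice. An unscoped counting rule adds a second choice, which affects severity and recurrence across the three sessions.

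**Working it through.** The plan gives no figure to reproduce, so the first two steps are a reading of the text. The third is an illustration.

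**Step 1: which reading do the documents favour?** Protocol 10.1 lists one severity and one onset date among the items recorded for each event. SAP 8.2.1 can impute a partly missing AE start date to the first dose date. Both point to classification by onset, but the SAP does not say so. Protocol 7.3.2 and 7.3.3 tell the therapy pair to assess the status of AEs already recorded, and Protocol 10.1.1 has AEs followed until they subside. Nothing in the documents asks for a new record when severity rises. Protocol 10.1.4 makes clinically significant worsening of a pre-existing condition reportable on the SAE/AESI form, but does not say how it enters the AE tables. Lesser worsening is not covered there.

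**Step 2: apply the readings to two hypothetical participants.**

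| Case | By onset | By presence | Onset-or-worsening definition |
|---|---|---|---|
| Mild anxiety in taper, severe the day after Session 1, one record | Pretreatment only | TEAE | TEAE, severe |
| Moderate insomnia in taper, unchanged after Session 1 | Pretreatment | TEAE | Pretreatment only |

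The onset reading is wrong for the first case and the presence reading for the second, so the two errors run in opposite directions.

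Now take severe insomnia in taper and a separate mild episode after Session 2. If the once-per-term rule works within each period, the tables show severe in pretreatment and mild in the TEAE table. If it spans periods, there is one severe record, and the text does not say which period holds it.

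**Step 3: what an unscoped rule would do to event counts.** Inputs: three sessions and about 100 participants (SAP 2.0). Assumptions, not in the documents: every participant has all three sessions, and a given term occurs at most once per session, independently, with probability p.

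- Events per 100 participants = 100 × 3p
- Records kept, if the rule spans sessions = 100 × [1 − (1 − p)³]
- Share not counted = 1 − [1 − (1 − p)³] / 3p

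| Assumed p | Events | Records kept | Share not counted |
|---|---|---|---|
| 0.1 | 30 | 27.1 | 10% |
| 0.3 | 90 | 65.7 | 27% |
| 0.5 | 150 | 87.5 | 42% |
| 0.6 | 180 | 93.6 | 48% |
| 0.7 | 210 | 97.3 | 54% |

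For p = 0.3: 1 − 0.7³ = 0.657, and 1 − 0.657/0.90 = 0.27. For p = 0.6: 1 − 0.4³ = 0.936, and 1 − 0.936/1.80 = 0.48. If everyone affected has the event at all three sessions, the share is 1 − 1/3 = 67%.

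The records-kept column is also the number of participants with at least one event. Incidence over the three sessions is therefore correct under the rule. Only the event count and the pattern of recurrence are lost.

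**The case against.** One record per participant per term at the highest severity is the ordinary convention for incidence tables, and the numbered AE objectives ask for incidence. The rule sits beside separate period categories and separate displays for the session day and the two days after, so the natural reading is one count within each table. On worsening, Protocol 10.1.4 does make significant worsening reportable. A site that entered it with a post-dose onset would put it in the TEAE window. The eCRF completion guide, which is not among the documents, may already require this. Protocol 4.2 has taper and washout completed before Visit 3, which limits overlap with dosing. SAEs, AEs of special interest, AEs leading to discontinuation, and C-SSRS results before and after dosing are tabulated separately, and listings are planned.

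Much of this stands, and it rules out several stronger readings that a reader might infer:

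- **That repeats are collapsed across the whole study.** The text states no scope, and silence is not a rule.
- **That event frequency is never counted.** SAP 8.8.2 promises to display it; only the definition is missing.
- **That the TEAE tables will misclassify taper symptoms.** They can, but whether they do, and in which direction, depends on the reading adopted and on site practice.
- **That nearly all participants taper.** Taper applies where needed, and no proportion is given.

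The objection does not supply a worsening criterion. Protocol 10.1.4 stops at reporting, and the separate tabulations do not settle which non-serious events belong in the TEAE table.

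**Conclusion.** The point holds as a gap in definition. The TEAE rule in SAP 8.8.2 can produce a wrong table in either direction for an event that starts before dosing and continues afterwards, and nothing else in the protocol or SAP resolves it. The number of events affected cannot be estimated, because the documents give neither the share of participants who taper nor AE rates.

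The counting rule is a lesser matter. Its scope is unstated and frequency is undefined, but participant incidence is not biased. The figures of 27% and 48% rest on assumed probabilities of 0.3 and 0.6, independence between sessions, and a rule applied across sessions to event counts. They show how far the answer could move under that reading and do not measure an error in the planned incidence tables.

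This should be fixed. It does not put the main conclusions of the study in doubt.

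**What to change.** Amend SAP 8.8 and 8.8.2, and Protocol 13.2.2 to match:

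1. Define a TEAE as an AE with onset at or after the first MDMA dose, or with earlier onset and an increase in severity after the first dose. Record that increase as a new AE entry with its own onset date, and say so in the eCRF completion instructions.
2. State that the once-per-term, highest-severity rule applies within each table's window (pretreatment; treatment period or session; Day 0, 1 and 2; follow-up) and to incidence only.
3. Define frequency as the number of events, and show it beside the number and percent of participants.

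The cost is a few sentences, slightly more data entry and one extra column per AE table. TEAE counts may rise. The change should be settled before database lock, and the recording instruction needs to reach sites while AEs are still being collected. For records already closed, the report should say whether a post-dose increase in severity can be recovered from source.
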